#### Annex 3.3 Definition of a Cardiovascular Event

### Cardiovascular Events (CV) Definition:

IC/ASA staff will be required to fill out the specific CV event page of the CRF for the following AEs and SAEs:

- Myocardial infarction/unstable angina
- Congestive heart failure
- Arrhythmias
- Valvulopathy
- Pulmonary hypertension
- Cerebrovascular events/stroke and transient ischemic attack
- Peripheral arterial thromboembolism
- Deep venous thrombosis/pulmonary embolism
- Revascularization

# Annex 3.4 Recording and Follow-up of AEs and SAEs

# AE and SAE Recording

- When a CABENUVA-related AE, AE leading to withdrawal, or any SAE occurs, it is the responsibility of the HIV care provider to review all documentation (e.g., hospital progress notes, laboratory and diagnostics reports) related to the event.
- The IC/ASA will then record all relevant AE/SAE (VOCABRIA or EDURANT related AEs, CABENUVA-related AEs, AEs leading to withdrawal, all SAEs) information.
- If an event is not an AE per definition above, then it cannot be an SAE even if serious conditions are met (e.g., hospitalization for signs/symptoms of the disease under study, death due to progression of disease, etc.).
- It is **not** acceptable for the IC/ASA or HIV care provider to send photocopies of the participant's medical records to the Medical Monitor or the Sponsor in lieu of completion of the eCRF required forms.
- There may be instances when copies of medical records for certain cases are requested. In this case, all participant identifiers, with the exception of the participant number, will be redacted on the copies of the medical records before submission.
- The IC/ASA staff, working with the HIV care provider, will attempt to establish a diagnosis of the event based on signs, symptoms, and/or other clinical information. Whenever possible, the diagnosis (not the individual signs/symptoms) will be

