#### 10.3.12. Cardiovascular and Death Events

All deaths will be reported and recorded as SAEs. In addition, all deaths will be required to have the eCRF death forms completed by the IC/ASA. These sections include questions regarding the death (including sudden cardiac death and non-cardiovascular death).

The Death eCRF is provided immediately after the occurrence or outcome of death is reported. Initial and follow-up reports regarding death must be completed within one week of when the death is reported.

For any CV events detailed in ANNEX 3, whether or not they are considered SAEs, specific CV sections of the eCRF will be required to be completed. These sections include questions regarding the CV event (including sudden cardiac death).

The CV CRFs are presented as queries in response to reporting of certain CV Medical Dictionary for Regulatory Activities (MedDRA) terms. The CV information should be

recorded in the specific cardiovascular section of the CRF within one week of receipt of a CV Event data query prompting its completion.

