#### **AE Definition**

- Exacerbation of a chronic or intermittent pre-existing condition including either an increase in frequency and/or intensity of the condition. If the IC/ASA staff are alerted to this, these events should be recorded.
- New conditions detected or diagnosed after CABENUVA administration at the IC/ASA that are considered CABENUVA related or lead to the discontinuation of CABENUVA even though it may have been present before the start of the study.
- Signs, symptoms, or the clinical sequelae of a suspected CABENUVA interaction.
- Signs, symptoms, or the clinical sequelae of a suspected overdose of CABENUVA or a contraindicated or concomitant medication with the potential drug-drug interactions. Overdose per se will not be reported as an AE/SAE unless it is an intentional overdose taken with possible suicidal/self-harming intent. Such overdoses should be reported regardless of sequelae.
- The signs, symptoms, and/or clinical sequelae resulting from lack of efficacy will be reported as AE or SAE if they fulfil the definition of an AE or SAE. "Lack of efficacy" or "failure of expected pharmacological action" also constitutes an AE or SAE.

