#### **Events NOT Meeting the AE Definition**

- Any clinically significant abnormal laboratory findings or other abnormal safety assessments which are associated with the underlying disease, unless judged by the HIV care provider to be more severe than expected for the participant's condition.
- The disease being studied or expected progression, signs, or symptoms of the disease/disorder being studied, unless more severe than expected for the participant's condition.
- Medical or surgical procedure (e.g., endoscopy, appendectomy): the condition that leads to the procedure is the AE.
- Situations in which an untoward medical occurrence did not occur (social and/or convenience admission to a hospital).
- Anticipated day-to-day fluctuations of pre-existing disease(s) or condition(s) present or detected at the start of the study that do not worsen.

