The seriousness of an AE will be independently assessed by the investigator from the severity of the AE. An SAE will be defined as any untoward medical occurrence that at any dose results in death, is lifethreatening, results in a congenital anomaly/birth defect, requires in-patient hospitalization or prolongation, or results in significant disability/incapacity. Important medical events that may not result in death, be life-threatening, or require hospitalization may be considered SAEs when, based upon medical judgment, they may jeopardize the participant and may require medical or surgical intervention to prevent one of the outcomes listed above. All SAEs will be presented in a table with the number and percentage of participants who experienced the event. The summary table will be displayed by SOC and PT.

Similarly, the following types of AE will be summarized in separate tables, if applicable:

- Baseline AEs reported at the Baseline/Month 1 visit beginning before informed consent and during the oral lead-in/injections that are considered related to oral CAB + RPV or the last CABENUVA injection
- Treatment-related AEs
- AEs leading to discontinuation
- Injection site reactions

- Cardiovascular events
- Liver monitoring/stopping events
- Pregnancy-related AEs
- COVID-19-related AEs

Other non-serious AEs that are considered not related to CABENUVA or do not lead to withdrawal are not documented in the eCRF, and therefore will not be summarized.

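### Annex 3.4 bars a death from HIV progression from being an SAE, Section 10.3.12 records every death as one, and nothing says which rule prevails

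*Protocol*

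**What the plan says.** The AE and SAE definitions are in Annex 3 of the protocol, and Section 10 sends site staff there for them.

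- **Annex 3.1, events that are not AEs:** the list includes "The disease being studied or expected progression, signs, or symptoms of the disease/disorder being studied, unless more severe than expected" for that participant.
- **Annex 3.4, recording:** "If an event is not an AE per definition above, then it cannot be an SAE even if serious conditions are met". Two examples follow in brackets: a hospital stay for signs or symptoms of the disease under study, and "death due to progression of disease, etc".
- **Section 10.3.12:** "All deaths will be reported and recorded as SAEs". It makes no exception by cause, and it requires the death pages of the eCRF as well.
- **Section 10.3.10, Table 3:** the row for a cardiovascular or death event calls for the AE/SAE eCRF plus the cardiovascular and/or death eCRF. A separate row gives 24 hours for all SAEs.
- **Clinical SAP, Section 4.7.1.1:** "An SAE will be defined as any untoward medical occurrence that at any dose results in death" or meets another listed criterion, among them in-patient hospitalization. It has no exclusion for disease progression. All SAEs go into a table of participant numbers and percentages.

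**The concern.** Two current rules give opposite answers for the same event. If a participant dies and the site or HIV care provider attributes the death to expected progression of HIV, Annex 3.4 says it cannot be an SAE and Section 10.3.12 says it must be recorded as one. About 35 infusion centers or alternate sites complete the eCRF, so similar deaths could be classified differently at different sites.

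The 24-hour SAE report and the SAP's SAE table are both driven by what the site enters as an SAE. The table would then partly reflect which page a site followed.

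**Working it through.** The plan states no figure on this point, so the check is a comparison of texts, followed by simple arithmetic for scale.

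**1. The route through Annex 3.** Annex 3.2 lists death as a seriousness criterion, but only for something that is already an AE. Annex 3.1 takes expected progression of the disease under study out of the AE definition. Annex 3.4 then says that what is not an AE cannot be an SAE, and names a progression death. Result: not an SAE.

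**2. The route through Section 10.** Section 10.3.12 makes all deaths SAEs, and Table 3 sends a death event to the AE/SAE form. Result: an SAE, due within 24 hours.

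**3. Does the qualifier reconcile them?** Annex 3.1 readmits progression that is more severe than expected. A site could argue that any fatal course is more severe than expected. But Annex 3.4 names the progression death outright as an event that stays excluded, so the qualifier does not remove the conflict. No order of precedence is stated.

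**4. Does the SAP reconcile them?** Its definition carries no progression exclusion, which brings it closer to Section 10.3.12. It can only tabulate what sites have entered, so it inherits any inconsistency.

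**5. What depends on the label.**

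| | If recorded as an SAE | If Annex 3.4 is followed |
|---|---|---|
| Time limit | 24 hours (Table 3) | one week for the death reports (Section 10.3.12) |
| Death form | yes | yes (Section 10.3.12 requires it for all deaths) |
| SAE table (SAP Table 14.3.10) | counted | not counted |

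The lists of tables and listings in SAP Section 7.3 name no separate output for deaths. The shells themselves are not in the text, so one could exist there.

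**6. Scale.** Let N be the size of the Safety Set. One reclassified participant with no other SAE moves the SAE percentage by 100/N points.

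- N = 120, the enrolment maximum: 100/120 = 0.83 points.
- N = 80 and N = 30, the ends of the low-enrolment range in Protocol Section 6.1: 100/80 = 1.25 and 100/30 = 3.3 points.

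The documents give no expected number of progression deaths. Assuming 0 to 2, the shift at N = 120 is 0 to 2 × 0.83 = 0 to 1.7 points.

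**The case against.** The best answer is that Section 10 deals with deaths specifically, in two places, while Annex 3.4 mentions them only as an example in brackets. A sensible site would follow Section 10. The death is captured on the death form in any case. The SAE table serves tertiary objectives: the primary endpoint is the FIM at Month 8, and the SAP says the sample size was not powered for clinical or safety outcomes.

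Much of this stands, and it keeps the point modest. It does not remove the conflict. Section 10 itself directs staff to Annex 3 for what counts as an AE or SAE, and the Annex 3.4 example names deaths just as explicitly as Section 10.3.12 does.

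A reader might also infer more than the documents support:

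- *That the SAP counts every death as an SAE.* It speaks of "any untoward medical occurrence that at any dose results in death". It drops the progression exclusion but does not say that all deaths qualify. That rule comes from Section 10.3.12.
- *That a hospital stay after loss of virologic control would go unrecorded as an SAE.* Annex 3.1 treats lack of efficacy as itself an AE or SAE and excludes only expected progression. Section 4.3 describes participants as virologically suppressed. A site reading Annex 3 as a whole can class the event as an AE, and the bar in Annex 3.4 then does not apply. The hospitalization example is awkward, but secondary.
- *That treatment failure would be hidden.* The SAP measures suppression and confirmed virologic failure from HIV-1 RNA (Section 4.7.4) and lists lack of efficacy among the discontinuation reasons (Section 4.3.1).
- *That about one such death should be expected.* The arithmetic would be 120 × 8/12 = 80 person-years, times an assumed 0.5 to 1.5 deaths per 100, giving 0.4 to 1.2. That rate is in neither document and covers deaths from any cause. Only those attributed to expected HIV progression are in dispute.

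**Conclusion.** The contradiction is real but narrow. For a death attributed to expected HIV progression, Annex 3.4 (through Annex 3.1) and Section 10.3.12 (with Table 3) cannot both be followed, and the documents do not rank them. Three things are left open: the SAE label, the 24-hour report and the line in the SAE table. The record of the death and the measurement of virologic failure do not depend on the label.

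The effect on the table is about 0.8 percentage points per affected participant. This assumes a Safety Set of 120 and no other SAE in that participant; the shift is larger if enrolment is low. The number of such deaths is unknown and may be zero. The case for acting is consistent reporting of serious events at little cost, not any risk to the study's main conclusions.

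**What to change.** Reconcile the passages in one of two ways.

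1. **If every death is meant to be an SAE:** add to the rule in Annex 3.4 *except that every death is recorded and reported as an SAE (Section 10.3.12)*, and refer to that exception from the progression exclusion in Annex 3.1.
2. **If a progression exclusion is meant:** state it in Section 10.3.12, in Table 3 and in the SAP's SAE definition.

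The amendment history describes the all-deaths statement as a clarification, and the Annex 3 definitions as moved in from the Study Reference Manual. That points towards the first option, but the sponsor must confirm it.

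Under either option, point the hospitalization example in Annex 3.4 to the lack-of-efficacy rule in Annex 3.1. Deleting the two examples alone would not be enough: the operative clause and the Annex 3.1 exclusion would remain, and together they would still conflict with Section 10.3.12.

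The first option costs about one sentence and a cross-reference, in an amendment or a memo to sites, and at most a few extra SAE entries. The second needs matching edits to the protocol and the SAP.

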#### AE and SAE Recording

documented as the AE/SAE and recorded in the eCRF if it is a VOCABRIA-, EDURANT, or CABENUVA-related AE, an AE leading to withdrawal, or an SAE.

#### Assessment of Intensity

All AEs and SAEs reported during the study should be evaluated by the IC/ASA physician, working with the HIV care provider, and if an AE/SAE is determined as a CABENUVA related AE, leads to discontinuation, or is an SAE, it will be graded in the eCRF.

The IC/ASA staff will capture the SAE causality in the participant's source notes in a timely manner, and the IC/ASA staff or an appropriately delegated team member will enter the causality into the eCRF. CRAs will monitor the participant source documentation to confirm that SAE causality is being documented in a timely manner.

- Mild: An event that is easily tolerated by the participant, causes minimal discomfort, and does not interfere with everyday activities.
- Moderate: An event that is sufficiently discomforting to interfere with normal everyday activities.
- Severe: An event that prevents normal everyday activities an AE that is assessed as severe will not be confused with an SAE. Severity is a category utilized for rating the intensity of an event, and both AEs and SAEs can be assessed as severe.

# **Assessment of Causality**

- The IC/ASA physician, working with the HIV care provider, is obligated to assess the relationship between CABENUVA and each occurrence of each AE and SAE reported. Prior to a participant enrolling in the study, if an AE or SAE should be reported and if it is related to oral VOCABRIA or EDURANT, it should be documented in the eCRF.
- A "reasonable possibility" of a relationship conveys that there are facts, evidence, and/or arguments to suggest a causal relationship, rather than that a relationship cannot be ruled out.
- The IC/ASA physician, working with the HIV care provider, will use clinical judgment to determine the relationship.
- Alternative causes, such as underlying disease(s), concomitant therapy, and other
  risk factors, as well as the temporal relationship of the event to CABENUVA
  administration, will be considered and investigated.
- The HIV care provider and/or IC/ASA physician will also consult the USPIs for CABENUVA, VOCABRIA, and EDURANT in their assessment
- For each AE and SAE, the IC/ASA physician must document in the medical notes that they have reviewed the AE/SAE and have provided an assessment of causality and have retrieved all required source documentation as available.

#### AE and SAE Recording

- There may be situations in which an SAE has occurred, and the IC/ASA has minimal information to include in the initial report to ViiV Healthcare (VHC). However, it is very important that the IC/ASA physician, working with the HIV care provider, always makes an assessment of causality for every event before the initial transmission of the SAE data to VHC.
- The HIV care provider may change their opinion of causality in light of follow-up information, and the IC/ASA should send an SAE follow-up report with the updated causality assessment.
- The causality assessment is one of the criteria used when determining regulatory reporting requirements.

### Follow-up of AE and SAE

- The HIV care provider will medically and clinically manage the follow-up of each AE and SAE. If this follow-up information is shared with the IC/ASA, this should be recorded. Information regarding the causality of the AE or SAE can be updated based on these investigations by the HIV care provider.
- If a participant dies during participation in the study, the IC/ASA will provide VHC with a copy of any postmortem findings including histopathology, if this is available to them.
- New or updated information will be recorded.
- The IC/ASA will submit any updated SAE data to VHC within 24 hours of receipt of the information.

# Annex 3.5 Reporting of SAEs to ViiV/GSK

#### SAE Reporting to ViiV/GSK via Electronic Data Collection Tool

- The primary mechanism for reporting SAEs to PPD and to VHC will be the electronic data collection tool.
- If the electronic system is unavailable, then the IC/ASA will use the paper SAE data collection tool to **report the event within 24 hours.**
- The IC/ASA will enter the SAE data into the electronic system as soon as it becomes available.
- The IC/ASA physician or a medically qualified sub-physician, working with the HIV
  care provider, must show evidence within the source documents of the review and
  verification of the relationship of each SAE to CABENUVA, VOCABRIA, or
  EDURANT.
- After the study is completed at a given site, the electronic data collection tool will be taken off-line to prevent the entry of new data or changes to existing data.

#### SAE Reporting to ViiV/GSK via Electronic Data Collection Tool

- If an IC/ASA receives a report of a new SAE from a study participant or receives updated data on a previously reported SAE after the electronic data collection tool has been taken offline, then the IC/ASA can report this information on a paper SAE form (see table below) or to the Medical Monitor by telephone.
- Contacts for SAE reporting can be found in SRM.

#### SAE Reporting to ViiV/GSK via Paper Data Collection Tool

- The IC/ASA staff will complete, scan, and upload the applicable AE/SAE or other safety event CRF to SharePoint and will then email Evidera/PPD and [contact] to inform them that an AE/SAE or other safety event has occurred and that the applicable form has been uploaded to the specific SharePoint folder. AE or SAE information must include the relationship to CABENUVA, and the IC/ASA will contact the participant's HIV care provider urgently to discuss this assessment.
- Evidera/PPD project managers (PMs) and the PPD Pharmacovigilance (PVG) team will receive automatic notifications when CRFs are uploaded and will review all AE/SAE and other safety event CRFs within one business day.
- Evidera/PPD PMs will contact the PPD PVG team to ensure that they have received the notification.
- The PPD PVG team will inform the GSK/ViiV medical monitor(s), safety team, and applicable team members of the event via email and will provide the necessary documentation within 24 hours of awareness. The GSK/ViiV medical monitors will be given access to the SharePoint site. The safety documents will be viewable through SharePoint and will not need to be downloaded.

#### **Annex 5: Protocol Amendments**

The Protocol Amendment Summary of Changes Table for the current amendment is located directly before the Table of Contents (TOC).

### Annex 5.1 Protocol Amendment 05 (14 November 2022

The primary and only purpose of this amendment is to update the Sponsor address on the Title Page

Section # and Name	Description of Change	Brief Rationale
Title Page	Updated Sponsor Address	Location Moved
Annex 5.1	Moved the Table of Changes from Protocol Amendment 04 to Annex 5.1	Moved according to the Protocol template

#### **Annex 5.2 Protocol Amendment 04 (6 October 2022)**

The primary and only purpose of this amendment is to update the Sponsor address on the Title Page

The primary purpose of this amendment is to support the additional Infusion Centers

The primary purpose of this amendment is to support the additional Infusion Centers being added to the study to broaden the geographical area within the US and to scale-up the implementation blueprint. The additional ICs will be initiated between approximately November 2022 – 1st Quarter 2023. Other changes include deletion of Exclusion Criteria 4 in Section 4.2.1 to allow participants into the study regardless of how many prior (pre-study) injections of CABENUVA they have received at the IC site and to remove the recruitment period of 12 months as the recruitment period for some sites may be longer than or less than 12 months.

Section # and Name	Description of Change	Brief Rationale
Global Change to Sections listed below	Added other clinical staff to also be allowed to complete questionnaires and interviews, represented as HIV Care Provider/clinical staff	Some HIV care providers manage their patients in conjunction with other clinic staff members who, work with ICs and may be better to complete some study assessments

 Global change to Section 1 Abstract, Section 2.1 Background, Section 2.2 Rationale, Section 3. Objectives and Endpoints, Section 4.1. Study Design, Section 4.3.2 HIV Care Providers, Section 5.1.2 Implementation Assessments, Section 5.1.3 Timepoint Definitions, Section 5.1.4 Primary Endpoint, Section 6. Statistical Considerations,

Section # and Name	Description of Change	Brief Rationale
l '	y Size, Section 6.2 Essential Ana 1 Schedule of Activities	alysis, Section 6.3 Secondary
Global Change to Sections listed below	Expert Panel expected completion is expected in late 2022	Clarification for the additional ICs, how the optimized blueprint and POT will be revised outside the Expert Panel
		Rationale, Section 4.1 Study on 5.1.1 Expert Panel, Section 5.1.5
Through-out	Minor editorial and document formatting revisions	Minor and therefore have not been summarized
Section 1 Abstract	Moved the Study Design section up within the abstract Added text regarding the additional ICs	Revised order for readability in light of the changes made Increased the approximate number of IC sites to include the additional ICs
	Removed all text regarding a 12-month recruitment period	The recruitment period for some sites may be longer than or less than 12 months
Section 4.1 Study Design	Modified schema	In the Participants design removed one set of the questionnaire/interview symbols for clarity  Added footnote to explain how the blueprint will be revised outside of the Expert Panel
Section 4.2 Study Population	Removed all text regarding a 12-month recruitment period	The recruitment period for some sites may be longer than or less than 12 months
Section 4.2.1.2 Exclusion Criteria	Removed Exclusion Criteria 4	To allow participants into the study regardless of how many prior (pre-study) injections of CABENUVA they have received at the IC
Section 4.3.2 HIV Care Providers	Revision to number of IC sites	Increased the approximate number of IC sites to include the additional ICs

Section # and Name	Description of Change	Brief Rationale
Section 4.3.3 Infusion Center Staff	Minor text changes	Clarification of text
Section 5.1.1 Expert Panel	Added text regarding the additional ICs entering the study	New information
Section 5.1.2 Implementation Assessments Section 6 Statistical Considerations	Added baseline analysis	To gain insights on the initial assessment of implementation science data on primary and key secondary objectives
Section 6.1 Study Size	Revision to number of IC sites	Increased the approximate number of IC sites to include the additional ICs
	Removed all text regarding a 12-month recruitment period	The recruitment period for some sites may be longer than or less than 12 months
Annex 1 Schedule of Activities	Corrected several errors in text and in the Month of assessment	Clarifications
Annex 5 Protocol Amendments	Moved Protocol Amendment 3 Table of Changes to Annex 5	

